9.2 Documenting and Reporting of Adverse Events (Including Serious Adverse Events)

Adverse events will be evaluated and documented using the grading scales contained in the National Cancer Institute Common Terminology Criteria for Adverse Events (NCI-CTCAE) Version 4.03.

9.2.1 Documenting and Reporting Adverse Events

All AEs reported from the time of informed consent to the EOS Visit for each subject will be recorded in the subject's source documents. For subjects who do not receive study drug (ie, alternates or screen failures), AEs will only be recorded in the source documents. For subjects enrolled into the study (ie, randomized), all AEs will be recorded in the subject's AE eCRF and the SAE Form (if applicable). The AE eCRF will indicate if the event occurred prior to the first dose of study drug, during treatment, or during the postdose Follow-up Period. The site should record all AEs regardless of the intensity, seriousness, or relationship to study drug.

Adverse events (serious and nonserious) will be graded in accordance with the NCI-CTCAE scale as follows:

- **Mild** (Grade 1): asymptomatic or mild symptoms; clinical or diagnostic observations only; intervention not indicated
- **Moderate** (Grade 2): minimal, local or noninvasive intervention indicated; limiting age-appropriate instrumental activities of daily living

- **Severe** (Grade 3): severe or medically significant but not immediately life-threatening; hospitalization or prolongation of hospitalization indicated; disabling; limiting self-care activities of daily living
- **Life-threatening** (Grade 4): life-threatening consequences; urgent intervention indicated
- **Death** (Grade 5): death related to the AE

Any recurrence of an AE with similar causality to study drug will be reported as recurrence or exacerbation of the initial event, and not as a new event. Whenever possible, AEs will be reported as a specific diagnosis or syndrome (eg, flu syndrome) rather than as individual signs or symptoms. If no specific diagnosis or syndrome is identified, AEs should be reported as separate and individual events.

An AE includes the following:

- Progression or exacerbation of the subject's underlying disease. Clinical sequelae that result from disease progression, such as pleural effusion or small bowel obstruction, are reportable as AEs
- Pre-existing event that increases in frequency or intensity
- Condition detected or diagnosed during the study period, even though it may have been present, in retrospect, prior to the first dose of study drug
- Laboratory abnormalities outside of normal limits with associated clinical symptoms or suspected latent clinical symptoms in the opinion of the Investigator, including those requiring therapeutic intervention
- An overdose of the study drug without any signs or symptoms will be considered an AE. A calculated dose that exceeds its correct dose by 10% or more and is administered to the subject will be considered an overdose and documented as an AE

The following events will not be identified as AEs in this study:

- Medical or surgical procedures (eg, surgery, endoscopy, tooth extraction, etc); however, the condition (the "triggering event") that leads to the procedure may be an AE
- Pre-existing conditions present or detected prior to the first dose of study drug that do not worsen

9.2.2 Assigning Attribution of Adverse Events

The Investigator must attempt to determine the cause of each event. Every effort will be made by the Investigator to assess the relationship of each AE to study drug. To ensure consistency of AE/SAE causality assessments, the Investigator should apply the following guidelines:

- **Related:** There is an association between the event and the administration of study drug, a plausible mechanism for the event to be related to the study drug and causes other than

the study drug have been ruled out, and/or the event reappeared on re-exposure to the study drug.

- **Possibly related:** There is an association between the event and the administration of the study drug and there is a plausible mechanism for the event to be related to study drug, but there may also be alternative etiology, such as characteristics of the subject’s clinical status or underlying disease.
- **Unlikely related:** The event is unlikely to be related to the study drug and likely to be related to factors other than study drug.
- **Not related:** The event is related to an etiology other than the study drug (the alternative etiology must be documented in the study subject’s medical record).

9.2.3 Classifying Action Taken With Study Drug

In the case of an AE, the actions that can be taken with study drug are defined in [Table 3](#).

Table 3: Options for Action Taken With Study Drug

Classification	Definition
Dose Not Changed	Study drug dose not changed in response to the adverse event
Drug Interrupted	Study drug administration interrupted in response to an adverse event
Drug Withdrawn	Study drug administration permanently discontinued in response to an adverse event
Not Applicable	Action taken regarding study drug administration does not apply. “Not applicable” should be used in circumstances when no opportunity to decide whether to continue, interrupt, or withdraw treatment was possible such as when the investigational treatment had been completed before the adverse event began.

9.2.4 Classifying Adverse Event Outcome

For every AE/SAE, the possible outcomes of the event and the definition of the outcome are shown in [Table 4](#). One outcome must be entered into the appropriate field on the AE and (if appropriate) SAE Form for each event as discussed in the eCRF instructions.

Table 4: Classification and Definition of Adverse Event Outcomes

Classification	Definition
Recovered/Resolved	Resolution of an adverse event with no residual signs or symptoms
Recovered/Resolved with sequelae	Resolution of an adverse event with residual signs or symptoms
Is Recovering/Is Resolving	Incomplete improvement to date but adverse event continues to improve/resolve and complete resolution is expected over time
Not Recovered/Not Resolved	Either incomplete improvement or no improvement of an adverse event, such that it remains ongoing
Fatal	Outcome of an adverse event is death. "Fatal" should be used when death is at least possibly related to the adverse event.
Unknown	Outcome of an adverse event is not known (eg, a subject lost to follow-up)

9.2.5 Documenting and Reporting Serious Pretreatment Events and Serious Adverse Events

All SAEs that occur after obtaining informed consent through the EOS Visit, regardless of causality, must be reported by the Investigator or designee to [REDACTED] and Enanta Pharmaceuticals, Inc. In addition, all SAEs, including those that result in death, that occur after the EOS Visit and that are considered related to study drug must be reported to [REDACTED] and Enanta Pharmaceuticals, Inc. within 24 hours of learning of its occurrence. Additional details are provided in the Safety Management Plan.

The SAE Form should be sent to [REDACTED]

All SAEs will be recorded on the SAE Form using a recognized medical term or diagnosis that accurately reflects the event. All SAEs will be assessed by the Investigator for severity, relationship to the investigational study drug, and possible etiologies. On the SAE Form, relationship to study drug will be assessed only as related or not related. For the purposes of study analysis, if the event has not resolved at the end of the study reporting period, it will be documented as ongoing. For purposes of regulatory safety monitoring, the Investigator is required to follow up the event to resolution and report the outcome of the event to [REDACTED] Enanta Pharmaceuticals, Inc. using the SAE Form.

The Investigator or designee is responsible for notifying the Sponsor within 24 hours of identifying an SAE, regardless of the presumed relationship to the investigational study drug. The SAE Form should be completed for new/initial events as well as to report follow-up

information on previously reported events. The Investigator or designee is asked to report follow-up information as it becomes available.

Enanta Pharmaceuticals, Inc. or its designees, as study Sponsor, is responsible for reporting suspected, unexpected, serious adverse reactions (ie, SUSARs) involving the study drug to all regulatory authorities, and participating investigators, in accordance with FDA, International Council for Harmonisation (ICH) guidelines, and/or local regulatory requirements, as applicable.

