4. STUDY DESIGN

This is a Phase 2b, randomized, double-blind, placebo-controlled, multicenter study of EDP-938 administered orally for the treatment of acute URTI with confirmed RSV infection in ambulatory adult subjects.

[figure not shown]
The study is composed of 3 periods:

- **Screening Period** will occur on Day 1. During this period, subjects will review and sign the Rapid Viral Screen ICF. Subjects will undergo a rapid diagnostic screen for RSV and influenza virus using respiratory secretions obtained by nasal (or nasopharyngeal) swab collection. Subjects whose swab sample tests positive for RSV and negative for influenza virus will review and sign the full study ICF and may proceed for further screening procedures. RSV positive and influenza negative subjects will be tested for SARS-CoV-2 at Screening and subjects who have positive test results for SARS-CoV-2 will be excluded from the study.
- **Treatment Period** will begin with the first dose of study drug on Day 1 and will conclude with the end-of-treatment (EOT) Visit on Day 5.
- **Follow-up Period** for safety will begin following the last dose of study drug and will conclude at the end-of-study (EOS) Visit on Day 14, 9 days following the last dose of study drug.

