4.1 Dose and Treatment Schedule

Subjects who meet all inclusion criteria and none of the exclusion criteria will be eligible to enter the study and will be randomized 1:1 to receive 800 mg of EDP-938 or placebo once daily for a total of 5 days. An overview of the study design is shown in [Figure 1](#). Study site visits and assessments are detailed in the Schedule of Assessments (SoA; [Appendix 1](#)).

Figure 1: Study Design

Abbreviations: d = day; FLU = influenza virus; RSV = respiratory syncytial virus.

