7.2.2 Procedures for Early Discontinuation or Early Termination of Treatment

Subjects who prematurely discontinue treatment early and have received at least one dose of study drug should return to the site within 24 hours and no more than 48 hours later and undergo the EOS procedures per the SoA ([Appendix 1](#)). Any subject who withdraws with ongoing AEs/SAEs should be followed up until resolution of their AE(s) or until the Investigator has determined that the AE(s) has stabilized.

Site staff will attempt to contact any subject who does not return to the site for the EOS Visit at least three times using the subject's preferred method of communication, followed by a letter requiring delivery notification if the three attempts were unsuccessful. Any subject who still cannot be reached following those attempts will be considered lost to follow-up. These subjects will be included in the PK and safety analysis as indicated in [Section 11.3](#).

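### AE and all-cause SAE collection ends at the EOS Visit, which early treatment stoppers have within 24 to 48 hours of stopping, so their new events up to Day 14 are not systematically collected

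*Protocol*

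**What the plan says.** Protocol 9.2.1 gives the AE window: "All AEs reported from the time of informed consent to the EOS Visit for each subject will be recorded". Section 9.2.5 gives the all-cause SAE window: "All SAEs that occur after obtaining informed consent through the EOS Visit, regardless of causality, must be reported by the Investigator or designee". For SAEs "that occur after the EOS Visit and that are considered related to study drug must be reported to" the sponsor, causality becomes a condition. Later in 9.2.5, another sentence makes the investigator responsible for notifying the sponsor within 24 hours of identifying an SAE whatever its presumed relationship, and gives no end date.

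Protocol Section 4 says that safety follow-up "will conclude at the end-of-study (EOS) Visit on Day 14, 9 days following the last dose of study drug"; SAP Section 1 repeats this. That describes a subject who completes dosing. For one who stops treatment after at least one dose, Protocol 7.2.2 says the subject "should return to the site within 24 hours and no more than 48 hours later and undergo the EOS procedures per the SoA". The synopsis, 7.1.2, 7.2 and footnote b of the Schedule of Assessments agree.

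Protocol 5.7.2, 7.2.2 and 8.6 use the term EOS Visit for the visit of subjects who stop early. Neither document schedules a contact after it, except follow-up of events already ongoing (7.1.3, 7.2.2, 9.3).

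**The concern.** Because collection closes at a visit, moving the visit forward moves the close of collection with it. A completer with a new, unrelated hospitalisation on Day 10 is inside the AE and SAE windows. A subject who stopped drug on Day 2 and has the same event on Day 10 is outside the AE window, and outside the all-cause SAE window as the opening sentence of 9.2.5 sets it.

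Adverse event and lack of efficacy are both listed reasons for discontinuation (Protocol 7.2.1), so the subjects with the shortest observation may be of particular safety interest. The AE summaries (Protocol 11.7.2, SAP 3.15.1) count subjects with events in the Safety Population and describe no allowance for observation time. SAP 3.15.1 puts no end date on treatment-emergent events, so whatever the protocol collects is what the tables contain.

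The stopping rules in Protocol 10.1 are also affected. One of them counts a single Grade 4 or higher AE in a subject receiving EDP-938 regardless of attribution. A new event of that grade, judged unrelated and occurring after an early EOS Visit, has no assured route to that review.

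**Working it through.** **Inputs**
- Planned dosing: "800 mg of EDP-938 or placebo once daily for a total of 5 days" (Protocol 4.1), so the planned last dose is on Day 5.
- End of follow-up for completers: Day 14 (Protocol 4), ±1 day (Schedule of Assessments).
- Early EOS: within 24 hours and at most 48 hours after stopping (Protocol 7.2.2).
- Dropout allowance: 20% of about 70 subjects (Protocol 11.2), not split by type.
- Assumption: stopping is declared either on the day of the last dose (lag 0) or when the next daily dose is missed (lag 1). The documents start the clock at discontinuation, not at the last dose.

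**Step 1: the plan's own figure.** 14 − 5 = 9 days after the last dose, as stated. With the ±1 day window it is 8 to 10.

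**Step 2: early treatment stoppers.** For a last dose on Day d (1 to 4):
- EOS day = d + lag + 1 (at 24 hours) to d + lag + 2 (at 48 hours)
- Observation after last dose = lag + 1 to lag + 2 days
- Days lost = 14 − EOS day

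| Last dose | EOS day, lag 0 | EOS day, lag 1 | Days lost to Day 14 |
|---|---|---|---|
| Day 1 | 2-3 | 3-4 | 10-12 |
| Day 2 | 3-4 | 4-5 | 9-11 |
| Day 3 | 4-5 | 5-6 | 8-10 |
| Day 4 | 5-6 | 6-7 | 7-9 |

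Collection therefore closes between Day 2 and Day 7. Observation after the last dose is 1-2 days with lag 0 and 2-3 days with lag 1. It can be slightly shorter, since 24 hours is an upper target and the visit may come sooner. Each such subject loses 7 to 12 of the 14 days.

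**Step 3: the whole trial.**
- Planned observation: 70 × 14 = 980 subject-days.
- Assumed dropouts: 0.20 × 70 = 14.
- All 14 stop during treatment: 14 × 7 = 98 to 14 × 12 = 168 days, which is 98/980 = 10.0% to 168/980 = 17.1%.
- Half (7) do: 7 × 7 = 49 to 7 × 12 = 84 days, which is 5.0% to 8.6%.

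Subjects who finish dosing and leave between Days 6 and 13 lose fewer days and are not in this calculation.

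**The case against.** The strongest reply is that the EOS Visit means Day 14. Protocol 4 and 7.1.3 define it that way, most of the early-stopping text speaks of EOS procedures rather than the EOS Visit, and the Schedule of Assessments marks AEs in every column to Day 14. This does not hold up: 5.7.2, 7.2.2 and 8.6 apply the term EOS Visit to early stoppers, and no contact after that visit is scheduled through which new events would be sought.

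Several other points do stand and limit the finding:
- A reader might infer that safety reporting stops altogether at an early EOS. It does not. Ongoing events are followed to resolution or stabilisation, a recurrence with similar causality is reported under the initial event (9.2.1), and related SAEs after EOS remain reportable.
- A reader might infer that an unrelated hospitalisation after an early EOS is definitely not reportable. The undated sentence in 9.2.5 could be read as requiring notice once the site learns of it. Section 9.2.5 also refers to a Safety Management Plan that is not among these documents. What can be said is that the rule is unclear and that nothing prompts the site to ask.
- A reader might infer that a 9-day follow-up promised to everyone is broken. The 9 days is Day 14 minus Day 5 and describes completers only.
- The 20% is a sample-size allowance, so treating every dropout as an on-treatment stopper in a 5-day course is an extreme case.
- Safety analyses are descriptive and AEs are not tested (Protocol 11.7, 11.7.2), so no inferential result is biased.

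**Conclusion.** The gap is real and follows from the text: for subjects who stop treatment early, new AEs and new SAEs judged unrelated are not systematically collected from about Day 2-7 to Day 14, while completers are observed to Day 14. This conclusion needs no assumption about dropout.

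Its size does. The 10-17% of subject-days is an upper guide that assumes all 14 allowed-for dropouts stop during treatment; 5-9% assumes half do. The documents give no number of on-treatment stoppers and no split by arm. It would go too far to say that the comparison between arms is biased. The supportable statement is conditional: because the tables count subjects with events without regard to observation time, uneven early stopping would distort the descriptive comparison. The change is worth making because it is cheap and because one stopping rule counts high-grade events regardless of attribution.

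**What to change.** 1. In Protocol 9.2.1 and 9.2.5, set the end of AE and all-cause SAE collection at Day 14 (±1 day) for every dosed subject who has not withdrawn consent, whether or not the EOS procedures were done earlier.
2. Add one Day 14 telephone contact, asking about AEs and SAEs, for subjects with an early EOS, and show it in the Schedule of Assessments.
3. Reconcile the two SAE sentences in 9.2.5, so that the window for all-cause reporting and the 24-hour notification requirement have the same stated end.

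The cost is a wording amendment and, on the assumed dropout, at most about 14 calls, with no added site visit or sample. For last doses on Days 1 to 4, collection to Day 14 gives 13 to 10 days after the last dose, which aligns the calendar end with completers rather than the 9-day interval. The call recovers nothing from subjects who are lost to follow-up or withdraw consent, so part of the loss will remain.

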9.2.6 Documenting and Reporting of Pregnancy

Subjects will be counseled to inform the Investigator of any pregnancy that occurs during study drug and for 90 days after the last dose of study drug.

If a female subject or the female partner of a male subject becomes pregnant while participating in the study, study drug must be permanently discontinued immediately. The Investigator or designee must notify [REDACTED], the Sponsor's Medical Monitor, and the [REDACTED] within 1 business day of the sites' knowledge of the subject's (or partner's) pregnancy, by utilizing the study-specified pregnancy report form. If confirmed to be on active drug, the subject or partner will be followed up until the end of the pregnancy and the infant will be followed up for 1 year after the birth, provided informed consent is obtained. A separate ICF will be provided to explain these follow-up activities. Pregnancy itself does not constitute an AE.

9.3 Follow-up of Adverse Events and Serious Adverse Events

All AEs (serious and nonserious) will be followed up until resolution or otherwise explained (see [Table 4](#)), the subject dies, the event stabilizes and is not expected to further resolve with the maximum time limit for stabilization defined as 30 days after the occurrence of the event, or when alternative therapy is instituted, whichever occurs first. If alternative therapy is instituted, it should be documented. Enanta Pharmaceuticals, Inc. may request that the Investigator perform or arrange for supplemental measurements or evaluations to further clarify the nature of the event.

9.4 Sponsor's Review of Adverse Events and Serious Adverse Events

Enanta Pharmaceuticals, Inc. will maintain an ongoing review of all AEs and SAEs.

9.5 Data Safety Monitoring Board

Safety data from this study will be reviewed by a DSMB throughout the study. The DSMB will be headed by a DSMB Chair and will include physicians with expertise in RSV, consisting of a group of 3 experts independent from the Sponsor. Procedures for data review, including timing and potential outcomes, roles and responsibilities, and interactions with the Sponsor and PPD, will be governed by a separate DSMB charter.

10. SUBJECT SAFETY MANAGEMENT/ STUDY STOPPING RULES

10.1 Study Stopping Rules

If any of these events occur, dosing will be placed on hold pending a full review of all available clinical safety data and discussion with the investigators and the DSMB.

- Two or more subjects receiving EDP-938 experience a similar Grade 3 study drug-related AE, including a confirmed treatment-emergent Grade 3 laboratory abnormality
- One or more subjects receiving EDP-938 experience a study drug-related SAE
- One or more subjects receiving EDP-938 experience Grade 4 or higher AE or a confirmed treatment-emergent laboratory abnormality regardless of causality attribution to study drug

10.2 Site or Study Discontinuation

10.2.1 Study Discontinuation

The Sponsor has the right to terminate this study at any time. Reasons for terminating the study may include, but are not limited to, the following:

- The incidence or severity of AEs in this study indicates a potential health hazard to subjects
- Subject enrollment is unsatisfactory
- Data recording is inaccurate or incomplete
- Investigator does not adhere to the protocol or applicable regulatory guidelines in conducting the study
- A decision from the IRB/EC or regulatory authority to terminate the study

If the study is suspended or terminated for safety reasons, Enanta Pharmaceuticals, Inc. will promptly notify the investigators and will also inform the regulatory authorities of the suspension or termination of the study and the reasons for the action. The Investigator is responsible for promptly informing the IRB/EC and providing the reasons for the suspension or termination of the study.

10.2.2 Site Termination

A single site may warrant termination under the following conditions:

- Failure of the site to enroll subjects into the study at an acceptable rate

- Failure of the site to comply with pertinent governmental regulations as appropriate
- Submission of knowingly false information from the research facility to the Sponsor, Clinical Monitor, or governmental authority
- Failure to adhere to the protocol requirements
- Data recording is inaccurate or incomplete
- Investigator does not adhere to the protocol or applicable regulatory guidelines in conducting the study

10.2.3 Study Termination Procedures

If the study is terminated by Enanta Pharmaceuticals, Inc. for one of the reasons listed previously, or upon completion of the study, the following activities must be conducted by the Study Monitor and/or site staff:

- Return of all study data to Enanta Pharmaceuticals, Inc. or designee
- Respond to and complete all requests for data clarifications
- Accountability and final disposition of used and unused study drug
- Review of site records for completeness
- Shipment of all applicable biological samples (including PK samples) to the designated laboratory

